#### **Secondary endpoints:**

• Time to ICU admission within 14 days of randomization

- Time to intubation and mechanical ventilation within 14 days of randomization
- Time to death within 14 and 28 days of randomization
  - Degree of improvement in oxygen saturation within 14 days of randomization
  - Improvement in respiratory symptoms of cough, shortness of breath, etc via respiratory symptom questionnaire within 14 days of randomization
  - Adverse events and conversion rates of COVID family members in CPAP vs control within 14 days of randomization
  - Percent of patients electing to continue CPAP for greater than 72 hours
  - Time to hospital admission or ED visit within 14 days of randomization

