#### REPORTS

For each DMC meeting, interim safety reports including reports of all mortalities, household COVID conversions, and adverse events will be prepared by the trial statistical team. In addition to the prescheduled meetings, the DMC Chair will receive and review reports of all mortalities, unexpected serious adverse events, and COVID conversions within 72 hours of the Investigator becoming aware of the event as well.

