#### 7.7 DAILY CHECKINS (DAYS 8-14, 28)

After 7 days, check-ins continue to occur daily. For patients on CPAP, the forms to be filled out are:

- Respiratory Questionnaire Form
- Interval Assessment Form
- Investigator Statement Form (Day 28)

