#### ADVERSE EVENTS

An AE is any unfavorable or unintended sign, symptom or disease occurring in a participant at any stage of the study, whether or not considered related to the study.

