#### CLINICAL ENDPOINTS

Any reported AEs that meet the following are also clinical endpoints and will be reported on the End of Study form. DMC Project Manager will review all AEs to determine if they also meet

clinical endpoint criteria. If criteria are met, the DMC Project Manager will ensure all documentation need for endpoint review is received by the site study coordinator.

	Anticipated A	Adverse Events (AAE)	Unanticipated Adverse Events (UAE)			
	
 
Headaches
 
	
 
Oxygen saturation less
 
	
 
Any Adverse effect
 
	
 
Any event that
 
		
	o Fever	than 90 during the	on the health or	results in death		
	o Chills	monitoring period	safety caused by, or	o Conversion of		
	
 
Loss of appetite
 
	
 
Absolute reduction in
 
	associated with, the	family members		
	o Nausea	oxygen saturation of more	CPAP or progression	to COVID		
	
 
Vomiting
 
	than 4% associated with	of underlying COVID	positive in the		
	o Fatigue	shortness of breath or	that was not	CPAP group		
	
 
Muscle or body aches
 
	difficulty breathing	previously identified			
	
 
New loss of taste or smell
 
	o Persistent pain or pressure	in the product			
	
 
Sore throat
 
	in the chest	labeling, published			
	
 
Congestion or runny nose
 
	
 
Any worsening of COVID
 
	literature or study			
	
 
Diarrhea
 
	symptoms that lead to an	protocol			
	
 
Decrease in oxygen
 
	Emergency room visit,				
	saturation (that is not	hospital admission, ICU				
	associated with shortness	admission, intubation, or				
	of breath or difficulty	mechanical ventilation				
	breathing)					
Reporting	None	Redcap	None	Redcap, DSMB, IRB		

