- Improvement in oxygen saturation will be compared between randomization groups using linear mixed-effect models with patient as a random effect.
- Improvement in respiratory symptoms, as measured by the Clinical COPD Questionnaire, will be compared between randomization groups using linear mixed-effect models with patient as a random effect.

Conversion rate of family members

The conversion rates (yes/no) of family members in the two randomization groups will be compared using a Fisher's exact test. If there is sufficient variability, a zero-inflated count model may be considered as well.

Continuation of CPAP for greater than 72 hours

The proportion of patients in the CPAP group who elected to continue CPAP use after 72 hours will be estimated along with 95% Coppler-Pearson confidence intervals.

Exploratory Analyses

Exploratory analyses will be conducted similarly as the primary analysis except that it will be only in the control arm comparing OSA versus non-OSA patents and obese vs non-obese patients.

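### The event table lists household COVID conversion for the CPAP arm only, although the plan compares it between arms, so control-household conversions may be under-ascertained

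*Protocol*

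**What the plan says.** Three places treat household conversion as a two-arm quantity.

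- Protocol section 1.3, Secondary endpoints: "Adverse events and conversion rates of COVID family members in CPAP vs control within 14 days of randomization".
- SAP, Conversion rate of family members: "The conversion rates (yes/no) of family members in the two randomization groups will be compared using a Fisher's exact test".
- Protocol section 3.1, under its reporting heading, says of the committee's scheduled reviews that "interim safety reports including reports of all mortalities, household COVID conversions, and adverse events will be prepared by the trial statistical team". Between meetings the DMC Chair also receives "unexpected serious adverse events, and COVID conversions within 72 hours of the Investigator becoming aware of the event". Neither sentence names an arm.

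One place does not. In the Clinical Endpoints table of section 10.2, the last column of unanticipated events, with the reporting route "Redcap, DSMB, IRB", holds two items. One is any event resulting in death, with no arm limit. The other is a family member becoming COVID positive, limited to the CPAP arm. Control households have no corresponding entry. The table is introduced with "Any reported AEs that meet the following are also clinical endpoints and will be reported on the End of Study form".

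**The concern.** Infection of household members by aerosol is a risk the protocol itself attaches to CPAP; it is the stated reason for the quarantine instruction in sections 1.2 (Study Design and Aim 1). The trial needs an even-handed count of it. If staff follow the section 10.2 table literally, a conversion in a CPAP household has a listed route into REDCap and on to the DSMB and IRB, and a conversion in a control household does not. Staff know the allocation, so nothing in the design would offset a difference in how hard conversions are looked for or filed. Any shortfall in control would push the comparison against CPAP, and at analysis a real excess could not be told apart from fuller recording. Control conversions not recorded at the time may not be recoverable later.

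**Working it through.** **Step 1. Can a control-household conversion enter by another route?**

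- *General adverse event route.* Section 10.2 says "An AE is any unfavorable or unintended sign, symptom or disease occurring in a participant at any stage of the study". A relative is not a participant, so this route does not cover the event.
- *Active surveillance.* Section 10.6 requires staff to seek adverse events, clinical endpoints and urgent referrals at each contact, in both arms. Section 10.2 ties clinical endpoints to its table, and the table's conversion entry is for CPAP only. Read literally, the duty to seek conversions has the same limit.
- *DMC reporting.* Section 3.1 is arm-neutral, but its 72-hour rule starts when the investigator becomes aware. It governs onward reporting and does not itself require anyone to ask.
- *Scheduled calls.* Section 7.1 has all patients called through day 14 and again on day 28. It mentions symptoms and saturation but not household status.
- *Forms.* No form named in sections 7.3 to 7.7 or in the Visits Figure is identified as recording household infection. The contents of the Follow-up Questionnaire and the Interval Assessment Form are not shown, so they may or may not ask about it.

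The arm limit is therefore real, and no visible passage clearly offsets it. Unequal capture is possible but not shown.

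**Step 2. Check of the method on the plan's own figures.** The documents give no rate, power or denominator for household conversion. The SAP does claim power above 80% for the primary endpoint with 100 per arm and a two-sided Fisher's exact test at 0.05. Exact power is the sum, over all pairs of counts (a, b) with Fisher p ≤ 0.05, of Bin(a; 100, p₁) × Bin(b; 100, p₂).

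| Control / CPAP | 0.25 / 0.09 | 0.30 / 0.12 | 0.35 / 0.16 | 0.40 / 0.20 | 0.45 / 0.25 | 0.50 / 0.29 |
|---|---|---|---|---|---|---|
| Exact power | 0.830 | 0.854 | 0.843 | 0.845 | 0.809 | 0.833 |

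The claim reproduces, so the same calculation is used below.

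**Step 3. What unequal capture would do.** All inputs here are assumptions except the type of test: one yes/no outcome per household, the same true rate p in both arms, full capture on CPAP, a captured fraction s in control, and a two-sided 0.05 level (which the SAP states only for the primary endpoint). The observed rates are then p on CPAP and p × s in control, and the apparent risk ratio is p / (p × s) = 1/s. For p = 20% and s = 0.65, control shows 0.20 × 0.65 = 13% and the ratio is 1/0.65 = 1.54.

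| Control capture s | Apparent risk ratio | p = 20%, 100 households per arm | p = 20%, 50 per arm | p = 10%, 100 per arm |
|---|---|---|---|---|
| 100% | 1.00 | 3.3% | 2.8% | 2.9% |
| 80% | 1.25 | 8.3% | 4.8% | 4.7% |
| 65% | 1.54 | 21.2% | 9.8% | 9.5% |
| 50% | 2.00 | 44.4% | 19.5% | 19.0% |

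The last three columns give the chance of a significant difference when none exists. One hundred households per arm is an upper limit, because section 5.2 admits patients who live alone. Fewer households lower the false-positive rate but leave the expected ratio of 1/s unchanged.

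**The case against.** The strongest reply is that the section 10.2 table classifies events and assigns reporting routes; it does not say which households are asked. Limiting expedited reports to CPAP households could be deliberate, since only there could a conversion be an unanticipated effect of the device. Contacts are arm-neutral where section 7.1 describes them, section 3.1 asks for household conversions without regard to arm, and the form contents are not shown. If no form records the item, that gap is the same in both arms. The capture fractions and true rates in the illustration have no source in the documents.

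Most of this stands, and it limits the point in four ways.

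- A reader might infer that control conversions are under-ascertained as a matter of fact. The documents do not show that; they show a rule that could produce it.
- A reader might infer that the DMC would see CPAP conversions with no comparable control rate. Section 3.1 is arm-neutral as written, so this does not follow.
- Section 7.7 introduces its form list with "After 7 days, check-ins continue to occur daily. For patients on CPAP, the forms to be filled out are", and gives no list for controls. A reader might infer that controls are not followed after day 7. Section 7.1 and the Visits Figure heading for days 8-14 and 28, which covers everyone, contradict that. It looks like a separate drafting slip, and no form on that list is shown to record household infection.
- A reader might want conversions counted beyond day 14. That is a preference about the window and has no bearing on the difference between arms.

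The reply does not remove the conflict. If the limit was meant only for expedited reporting, the protocol does not say so: the same cell also governs entry in REDCap and, through the table's introduction, what counts as a clinical endpoint.

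**Conclusion.** The point holds as a conflict in the text with a credible risk of bias. The CPAP-only entry in section 10.2 does not fit the between-arm endpoint in section 1.3, its test in the SAP, or the arm-neutral DMC reporting in section 3.1. If control conversions are captured less often, the bias runs against CPAP, and open-label conduct makes that more plausible.

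The size cannot be derived from the documents. Under the stated assumptions at a 20% true rate, control capture of 80% to 50% gives an apparent risk ratio of 1.25 to 2.0. The false-positive rate is 8% to 44% with 100 at-risk households per arm and 5% to 19% with 50, against about 3% with equal capture. These figures show how sensitive the comparison is; they do not predict what this trial would see. The primary endpoint and the sample size are not affected.

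**What to change.** 1. In the section 10.2 table, remove the limit to the CPAP arm, so that a conversion in either arm is recorded in REDCap and enters DMC reports in the same way. If a CPAP-only limit is intended for expedited DSMB and IRB reports, state that it applies to those reports alone.
2. Put the same household-conversion question to both arms, at the same calls, through day 14, and name the form that holds the answer.
3. As a minor consistency edit, reconcile the form list in section 7.7, which is worded for CPAP patients, with section 7.1 and with the Visits Figure column for days 8-14 and 28.

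The cost is protocol wording, one question on existing calls and a few more reports from control households.

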#### 1.4 STUDY PHASES

#### SCREENING PHASE

Eligible participants will be identified by:

- 1) **Precision Recovery Program.** This program is a Sinai-wide initiative which is remotely monitoring patients who are sent home from the emergency room. This is similar to our protocol and therefore working with the precision recovery program will be a synergistic effort. **We will exclusively recruit from their pool of patients when possible**, as the precision recovery program will hand out our fliers to their participants, and therefore will ensure that the patient does not get a cold call from us.
- 2) **Emergency room staff members.** Members of the research team (primarily Emergency Room department, in these following two locations: main ED, and surge space (Martha Stewart)) will identify and provide flyers to the patients as discussed above.
- 3) Via EPIC screening. Subjects will also be identified using the EPIC database of COVID confirmed/suspected patients lists to see if patients meet our inclusion criteria.

At the time of introducing the study to the patient, the inclusion/exclusion criteria will be reviewed by the study team member.

#### ENROLLMENT PHASE

For all participants, this phase occurs from the time of consent through on average a period of about 28 days. All participants will be followed until their 28 day participation. Procedures are outlined in the "Study Procedures" section. The enrollment phase may continue past these points for participants requiring ongoing monitoring of an AE.

#### CLOSE-OUT PHASE

The closeout phase includes confirming that all queries are addressed, the dataset is finalized, locked and analyzed, all documentation is appropriately stored, and the study is closed with the Institutional Review Board (IRB).

#### 1.5 PROTOCOL AMENDMENTS

The objectives of the PAP-COVID study are most likely to be achieved if the protocol does not require alteration. Any changes in the protocol would result in some degree of heterogeneity of the data, which may complicate the analyses and may compromise the scientific integrity of the study. However,

occasions may arise in which protocol changes are necessary. Therefore, changes in the protocol will be considered only if they are required to ensure safety or will significantly enhance the scientific validity or feasibility of the study. Any member of the PAP-COVID study team may request a change to any portion of the study protocol. The staff member wishing to change the protocol should present the proposed changes(s) in writing to the PI, who will then contact other relevant personnel. The Executive Committee will then jointly decide on the appropriate mechanism (letter, conference call, or meeting) to handle the proposal depending on the implications of the proposed change. Proposed changes will be presented to all study members via conference call or formal meeting to allow all members to benefit from the scientific debate generated in these discussions. Proposed changes can be implemented only after the PI and relevant personnel reach a majority vote. Once a proposed change has been approved, the Research Manager will coordinate all activities required to implement the change via the issuance of a protocol amendment document and revised protocol. Substantive changes to the protocol and ancillary proposals must be submitted to the Data Monitoring Committee (DMC) for review and approval before implementation can occur.

#### 2 – STUDY ORGANIZATION

#### 2.1 PROJECT MANAGEMENT

[figure not shown]

#### 2.2 MEETING SCHEDULES

Each of the major committees will meet on a regular basis: Usual meeting (by phone or video conference) intervals are as follows, but may vary at the discretion of the Chair, depending on the study needs:

- Executive Committee: Every two weeks by conference/Zoom call
- Research Operations: Every week by conference/Zoom call
- Data Management: Monthly or more frequent intervals, as needed, by conference/Zoom call
- Clinical Oversight: Monthly or more frequent intervals, as needed, by conference/Zoom call
- Data Monitoring Committee: The DMC will meet prior to trial initiation to discuss the Charter, review and approve the study protocol prior to study initiation, review any other relevant documents, and make recommendations to the sponsor and study team regarding possible modifications. Future meetings will review the accumulating data on safety and, study quality and will be scheduled approximately three times during the course of the trial (after 25%, 50% and 100% of patients reach the primary endpoint at 14 days post-randomization). Meetings will be conducted via zoom. A DMC meeting will require a quorum.

To aid communication, a study OneDrive will be developed which will include areas for posting study documents, interactive study progress reports, quality control reports, and a publications hub.

#### 2.3 CLINICAL SITES

Subjects are at-home patients discharged or denied entry to the ER at any Mount Sinai hospital. All study contact (ie. recruitment, consent, explanation of study procedures) will occur remotely via telephone and video calls. Study devices will be shipped to the patients' home. The patient will then use the devices in their own homes.

#### 3 – STUDY OVERSIGHT

#### 3.1 DATA MONITORING COMMITTEE (DMC)

#### DESCRIPTION

This Charter is for the Data Monitoring Committee (DMC) for the Early Continuous Positive Airway Pressure (CPAP) in COVID Confirmed or Suspected Patients study (PAP-COVID Study).

This Charter defines the primary responsibilities of the DMC, it's relationship with other trial components, its membership, and the purpose and timing of its meetings. The Charter also provides the procedures for minimizing conflicts of interest and ensuring confidentiality of emerging data and deliberations of the DMC, as well as statistical monitoring guidelines to be considered by the DMC, if any. It will also address the content of the Open and Closed Reports that will be provided to the DMC.

#### REPORTS

For each DMC meeting, interim safety reports including reports of all mortalities, household COVID conversions, and adverse events will be prepared by the trial statistical team. In addition to the prescheduled meetings, the DMC Chair will receive and review reports of all mortalities, unexpected serious adverse events, and COVID conversions within 72 hours of the Investigator becoming aware of the event as well.

#### ADDITIONAL INFORMATION

More information regarding DMC membership, responsibilities, and operations can be found in the DMC Charter (separate document).

#### 3.2 INSTITUTIONAL REVIEW BOARD

This study is to be conducted according to U.S. and international standards of good clinical practice, applicable government regulations and institutional research policies and procedures. The final study protocol and any amendments will be submitted to the IRB and Mount Sinai COVID-19 Research Protocol Committee. The decision of the IRB concerning the conduct of the study will be made in writing to the PI and a copy of this decision will be provided to the sponsor before commencement of this study.

#### 4 – SCREENING AND RECRUITMENT

#### 4.1 SCREENING AND RECRUITMENT OVERVIEW

Overall recruitment should focus on patients with known or suspected COVID-19 who are experiencing symptoms, and have been discharged from or denied admission to the ED.

#### 4.2 RECRUITMENT SOURCES

[figure not shown]
Eligible participants will be identified by:

- 4) **Precision Recovery Program.** This program is a Sinai-wide initiative which is remotely monitoring patients who are sent home from the emergency room. This is similar to our protocol and therefore working with the precision recovery program will be a synergistic effort. **We will exclusively recruit from their pool of patients when possible**, as the precision recovery program will hand out our fliers to their participants, and therefore will ensure that the patient does not get a cold call from us.
- 5) **Emergency room staff members.** Members of the research team (primarily Emergency Room department, in these following two locations: main ED, and surge space (Martha Stewart)) will identify and provide flyers to the patients as discussed above.
- 6) Via EPIC screening. Subjects will also be identified using the EPIC database of COVID confirmed/suspected patients lists to see if patients meet our inclusion criteria.

#### 4.3 SCREENING PROCEDURES

EPIC screening procedures are as follows:

[figure not shown]
1) Click on Epic logo dropdown top left corner

[figure not shown]
2) Reports  $\rightarrow$  My Reports

- 3) Click Library left hand side
- 4) Search "COVID"

- 5) "Star" COVID-19 Confirmed Prior thru Current Discharges by sites
  - a. This shows you positive discharge patients

- 6) "Star" COVID-19 Confirmed Prior thru Current
  - a. This shows all COVID from MSH
- 7) "Run" the report
- 8) Open patient chart, go to Notes, and read ED Provider Notes (symptoms)
  - a. Check for inclusion/exclusion criteria in chart
    - i. (ALL EXCLUDED PATIENTS ADD TO RIPPLE, add note for exclusion)
  - b. Call patient to see if interested

#### Once contacted patient,

[figure not shown]
- 1) If interested, input in OnCore and begin study
- 2) If not interested, add to Ripple and add a note saying not interested

#### **Dashboard (MSH COVID Statistics)**

 $EPIC \rightarrow Reports \rightarrow My dashboards$ 

- 1) My dashboards
- 2) Search: "MSH COVID-19 Monitoring"

- 3) Star "MSH COVID-19 Monitoring Dashboard"
- 4) Run report
- 5) Scroll down to bottom, click "MSH ED SURGE"
- 6) Double click to see patients

#### 4.4 RECRUITMENT AND RETENTION OVERSIGHT

#### RECRUITMENT TRACKING

Tracking will occur through online software: Oncore and Ripple. Patients who enroll will be tracked in Oncore. Patients who decline to enroll, or are ineligible will be recorded in Ripple to prevent double calling.

#### 5 – PARTICIPANT POPULATION AND ELIGIBILITY

#### 5.1 DESCRIPTION OF POPULATION

This study will involve participation of adults with confirmed or suspected COVID-19 and abnormal chest X-ray or clinical symptoms. Adults  $\geq$  18 years of age, of both genders and all racial and ethnic groups will be eligible for participation. Inclusion and exclusion criteria refer to the participant only.

#### 5.2 ELIGIBILITY CRITERIA

Eligibility criteria are listed on the Eligibility [ELIG] CRF, and below.

#### INCLUSION CRITERIA

- 1. Adults > 18 years old
- 2. Patients living alone or with more than one room at home
- 3. COVID-19 confirmed or suspected
- 4. To be discharged home or already discharged
- 5. One or more of these: fever (>38°C), sore throat, myalgia or flu-like illness
- 6. One or more of the following: abnormal chest x-ray, new onset cough, mild hypoxemia (saturation between 92-96%), abnormal lung exam, chest tightness or shortness of breath

